10. PUBLICATION POLICY

Our aim is to ensure the full dissemination of all study results in medical publications of the highest impact and citation factor. Individual subjects will be strictly anonymised.

Appendix 1: Schedule of Events: Summary of Screening Procedures

Depending on the part of the study, a range of these procedures will be performed.

	Pre-challenge
Telephone screening	X
Clinical history	X
Physical exam	X
Skin allergen test	X
Tuberculin skin test	X
Interferon-gamma release assay (IGRA)	X
FBC, U&E, LFT, IgE	X
Chest X-ray and ECG	X
Informed Consent	X
Nasal and Pharyngeal Swab Sample	
Calcium, 25-OH Vitamin D levels, melatonin	X
Pregnancy test (if applicable)	X
Methacholine bronchoprovocation	X

Appendix 2a: Summary of Procedures for Nasal Toll-Like Receptor (TLR) Agonist Challenge

PART A: Incremental Ascending Dose Study based on Tolerability and SAM

Time 2a	Total duration = 30 min Nasal sampling before NC			Nasal Challenge (NC)	Total duration=9h Hourly nasal sampling post NC				
	-30m	-20m	-10m		15m	30m	45m	1h	2h – 8h
Nasal challenge Saline/TLR agonist (variable doses)				X					
Nasal lavage (Washing only)		L/R							
Nasal mucosal examination	X				X	X	X	X	X
Total nasal symptom scores (TNSS) & PNIF	X				X	X	X	X	X
Nasosorption (L and R)	L/R		L/R		L/R	L/R	L/R	L/R	L/R

- LEFT nostril: Nasosorption neat: to include from lipidomics, mass spectrometry, prostanoids, PGD2, tryptase
- RIGHT nostril: Nasosorption in assay buffer: for chemokines and cytokines, complement C3a & 5a

Appendix 2b: Summary of Procedures for Nasal Toll-Like Receptor (TLR) Agonist Challenge

PART B: Highest Dose (1000µg over 1h, or highest single dose)

Time 2b	Screening	Total duration = 30 min Nasal sampling before NC			Total duration = 1h Nasal Challenge (NC) 200µg/nostril on 5 occasions over 1h					Total duration=8h Hourly nasal sampling post NC					Total duration = 2h
	D -7	-30m	-20m	-10m	0m	15m	30m	45 m	60m	75m	90m	105m	120m	3h – 9h	24h
Nasal challenge Saline / TLR agonist					X	X	X	X	X						
Nasal lavage (Washing only)	X		L /R												
Nasal mucosal examination		X				X	X	X	X	X	X	X	X	X	X
Total nasal symptom scores (TNSS) & PNIF		X				X	X	X	X	X	X	X	X	X	X
Nasosorption (NS)		L /R		L /R						L /R	L /R	L /R	L /R	L /R	X
Nasal curettage	X Up to 4 samples													(9h) 4L	X 4R
Blood (20ml)			X												X
OPTIONAL: Nasal SSP (Real time MS)		X	X	X	X	X	X	X	X	X	X	X	X	X	X

- LEFT nostril: Nasosorption neat: to include from lipidomics, mass spectrometry, prostanoids, PGD2, tryptase
- RIGHT nostril: Nasosorption in assay buffer: for chemokines and cytokines, complement C3a & 5a

Appendix 2c: Summary of Procedures for Nasal Resiquimod Challenge

PART B: Highest Dose (10µg/100µl)[Jan 2016: move to a weight based dosing regimen between 0.02µg/kg to 0.05µg/kg]

Time 2c	Screening	Nasal sampling before NC Total duration = 30 min			Nasal Challenge (NC)	Hourly nasal sampling post NC Total duration=8h					Final Sample
	D -7	-30m	-20m	-10m	0m	15m	30m	45m	60m	1-10h	24h
Nasal challenge Saline / Resiquimod					X	X	X	X	X		
Nasal lavage (Washing only)	X		L /R								
Nasal mucosal examination		X				X	X	X	X	X	X
Total nasal symptom scores (TNSS) & PNIF		X				X	X	X	X	X	X
Nasosorption (NS)		L /R		L /R		L /R	L /R	L /R	L /R	L /R	X
Nasal curettage	X Up to 4 samples									(6-8h) 4L	X 4R
Blood (up to 20ml)	X		X							X (4h) X (8h)	X
Spirometry (for asthmatics)	X	X								1,2,4,8h	x

Appendix 3a: Part A Summary of Procedures for Tuberculin Nasal Challenge

PART A: Nasal ascending dose (0.1TU, 1.0TU, 2.0TU, 5.0TU) tolerability and SAM

Time 3a	S D -7	-30m	-20m	-10m	Nasal Challenge (NC)	1h – 8h	d1	d2	d3	d4	d7
Nasal challenge Saline/Tuberculin (variable doses)					X	X					
Bilateral nasal lavage for washing purposes	X		X			X					
Nasal mucosal examination		X				X	X	X	X	X	X
Total nasal symptom scores (TNSS) & PNIF		X				X	X	X	X	X	X
Nasosorption		X 2L 2R		X 2L 2R		X 2L 2R	X 2L 2R	X 2L 2R	X 4L	X 4R	X 4R
OPTIONAL Nasal curettage	X							X 4R		X 4L	X 4R

- LEFT nostril: Nasosorption neat: to include from lipidomics, mass spectrometry, prostanoids, PGD2, tryptase
- RIGHT nostril: Nasosorption in assay buffer: for chemokines and cytokines

Appendix 3b: Part B Summary of Procedures for Tuberculin Nasal Challenge

PART B: Top dose (10.0TU) with Additional Sampling

Time 3b	S D-7	-30m	-20m	-10m	Nasal Challenge	1h – 8h	d1	d2	d3	d4	d7
Nasal challenge Placebo/Tuberculin (Top dose)					X						
Bilateral nasal lavage for washing purposes	X		X								
Nasal mucosal examination		X				X	X	X	X	X	X
Total nasal symptom scores (TNSS) & PNIF		X				X	X	X	X	X	X
Nasosorption		X 2L 2R		X 2L 2R		X 2L 2R	X 2L 2R	X 2L 2R	X 4L	X 4L	X 4R
Nasal curettage	X							X 4R		X 4L	X 4R
Blood (20ml)		X						X		X	X
OPTIONAL Nasal SSP							X				

- LEFT nostril: Nasosorption neat: to include from lipidomics, mass spectrometry, prostanoids, PGD2, tryptase
- RIGHT nostril: Nasosorption in assay buffer: for chemokines and cytokines

**Appendix 4A: Vitamin D3 in Nasal Allergic Rhinitis (ViDAR)
Summary of Procedures for Nasal Allergen Challenge (NAC) Days**

Procedure	-30m	-20m	-10m	Nasal Challenge	5m	15m	30m	45m	1h	Hourly 2-8h
Nasal allergen challenge Timothy grass pollen Phleum P5				X ~ 9AM						
Bilateral nasal lavage for washing purposes (discard)		X								
Oral capsule: Day 28: vitamin D or placebo	X									
Total nasal symptom scores (TNSS) and peak nasal inspiratory flow (PNIF)			X		X	X	X	X	X	X
Nasosorption (SAM)	L/R		L/R		L/R	L/R	L/R	L/R	L/R	L/R
Blood (75ml)*	X									
Nasal curettage (rhinoprobe)										2L/2R At 8 hours (~5PM)

*Blood for full blood count (5ml); peripheral blood mononuclear cells (PBMC) (50ml); serum vit D, calcium, cortisol, melatonin (10ml); whole blood transcriptomics (10ml)

Appendix 4B: Summary of Procedures for Nasal Allergen Challenge (NAC)

Time 4	-30m	-20m	-10m	NC	5m	10m	15m	30m	45m	1h	2h	3h	4h	5h	6h
Nasal challenge Saline/Allergen				X											
Bilateral nasal lavage for washing purposes		X													
Nasal mucosal examination	X		X		X	X	X	X	X	X	X	X	X	X	X
Total nasal symptom scores (TNSS) & PNIF	X				X		X	X	X	X	X	X	X	X	X
Nasosorption	X 2L 2R		X 2L 2R		X 2L 2R	X 2L 2R	X 2L 2R	X 2L 2R	X 2L 2R	X 2L 2R	X 2L 2R	X 2L 2R	X 2L 2R	X 2L 2R	X 2L 2R
Blood	X														X
Nasal curettage	X 4L														X 4R
OPTIONAL Nasal SSP	X	X	X	X	X	X	X	X	X	X	X	X	X	X	X

- LEFT nostril: Nasosorption neat: to include from lipidomics, mass spectrometry, prostanoids, PGD2, tryptase
- RIGHT nostril: Nasosorption in assay buffer: for chemokines and cytokines

Appendix 5: Pharmaceutical Quality of Agents delivered by Nasal Spray as Nasal Challenges or taken orally

Challenge/Oral Agent	Manufacturer Contact person	Catalogue Dose	Production Purity

Timothy grass pollen allergen licensed for intraepidermal and subcutaneous skin testing
 
Aquagen SQ Timothy grass Pollen Phleum pratense number 4
	
Manufacturer: ALK-Abello: [contact] [name] [contact] MOB [name] [contact]
 
Supplier: Healthcare Logistics [contact], [name].
	
Aquagen SQ Timothy grass Pollen, internal code 1001862 product code 225 156 (ALK 225)
	
ALK Abello freeze dried extract.

Tuberculin purified protein derivative (PPD) licensed internationally for intradermal skin testing In the Mantoux test
		
 • 20 units/ml, 1.5ml vial • 100 units/ml, 1.5ml vial 	
Heat-treated products of growth and lysis of appropriate Mycobacterium spp.

Poly-ICLC (poly inosine-cytosine stabilised with poly-L-lysine)
 
Hiltonol Vaccine component (HTN code 3002200) Registered with FDA under IND 43984, held by Oncovir Inc. Lot PJ215-10-01
	
Dalton Chemical Laboratories for Oncovir
 
[name] CEO & Scientific Director Oncovir, Inc., [name] [contact]
 
[contact]
	
2mg/ml 1ml/vial
	
Chemical synthesis. Non-biological origin: does not contain any animal nor human components


Poly-IC (inosine-cytosine), high molecular weight, ultrapure Synthetic analogue of double stranded RNA
	
Invivogen, California [name] www.invivogen.com
	
Tlr1-pic 10mg and 50mg Lyophilised powder
 
Reconstitute in endotoxin-free physiological water
	
Chemical synthesis. Non-biological origin: does not contain any animal nor human components Endotoxin level <1.25 EU/mg

MPLA (monophosphoryl lipid A) Synthetic vaccine grade
	
Invivogen, California [name] www.invivogen.com
	
1 mg MPLA VacciGrade supplied as a clear lipidic film. CAS 1246298-63-4 Reconstitute in endotoxin-free physiological water
	
Chemical synthesis. Non-biological origin: Comprises lipid A from E.coli serotype R515, with 6 fatty acyl groups

Resiquimod R848 VacciGrade TLR 7/8 agonist Synthetic vaccine grade
	
Invivogen, California [name] www.invivogen.com
	
5 mg lyophilized R848 Reconstitute in endotoxin-free physiological water CAS 144875-48-9
	
Non-biological origin: does not contain any animal nor human components. Endotoxin <1.25 EU/mg

Vitamin D3	Vitamin D3 from Lamberts Healthcare Ltd http://www.lambertshealthcare.co.uk	4000IU	Manufactured according to GMP & meets British Pharmacopoeia (BP) standards for Vitamin D levels
-------------------	---	--------	--

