APPENDIX 2C

Appendix 2C

Nasal Challenge with Resiquimod (TLR7/8)

Part B. 0.02µg/kg to 0.05µg/kg with Blood Sampling and Nasal Curettage

Single Cohort of up to 46 Volunteers

(12 non-atopic; 12 atopic, 16 allergic asthma, 6 non-allergic asthma)

Each subject given saline control and between resiquimod 0.02 µg/kg to 0.05µg/kg per nostril
4 subjects with asthma initially given half the dose of healthy volunteers

Safety Observations

Nasal mucosal exam, nasal & systemic symptoms and spirometry checked hourly until 10h and at 24h

Screening

- Skin AG pricks
- ECG
- Blood DNA
- Nasal curettage
- Bloods
- Nasal/pharyngeal swab

d-7

Nasal Challenge Saline

d0

Nasal Challenge Resiquimod 0.02 µg/kg to 0.05 µg/kg

d7

Repeat Nasal Challenge (up to 6 from each group) 0.02 µg/kg to 0.05 µg/kg

>6 weeks

Nasal Challenge Procedures

- Initial bilateral lavage at -20m
- PNIF and nasal symptoms: -30m, 15m, 30m, 45m, 1-24h
- Nasal SAM: -30m, -10m, 15m, 30m, 45m, 1-24h
- Nasal curettage: d-7, 8h and 24h (up to 4/timepoint)
- Blood up to 20ml x4: -20m, 4h, 8h & 24h

Nasal SAM, neat:

- Mass Spectrometry
- Lipidomics
- Prostanoids

Nasal SAM, eluate:

- Cytokines & chemokines

Nasal curettage:

- Flow cytometry & transcriptomics

Blood

- Flow cytometry

P
V

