3.1 STUDY OUTCOME MEASURES

- Clinical symptoms and tolerability
- Inspection of nasal mucosa by a clinician: erythema, discharge, ulceration
- Mucosal lining fluid cytokines and chemokines
- Blood and nasal flow cytometry and transcriptomics
- Nasal lining fluid metabolites

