7. STATISTICS AND DATA ANALYSIS

Data and all appropriate documentation will be stored for a minimum of 10 years after the completion of the study, including the follow-up period.

The major data will be levels of cytokines and chemokines in nasal SAM eluates.

We shall perform a test of distribution of data (Shapiro-Wilks test), although nasal levels of chemokines and cytokines are generally non parametric in distribution.

Raw Data:

We shall make plots for individual cytokines with raw data for individuals connected by lines. These “spaghetti plots” generally have different colours for different individuals.

Summary Statistics

Normal data with graphs with means and standard error of means (SEM)

Non-normal data with graphs with medians, quartiles and ranges (box-whisker)

Non-parametric tests are used to compare challenge effects with placebo at different times:
Willcoxon signed-rank test for paired and Mann-Whitney for unpaired data.

The differences from baseline and difference compared with that from placebo (active-placebo) at each time point and the differences from placebo (active-placebo) will be calculated, and the significance determined.

We shall also analyse area under the curve (AUC), by selecting specified times in the early or late phase or for the entire response.

e.g. PGD2 from 10min to 2h

e.g. for IL-4 at 4 to 8h.

A *P* value of <0.05 is considered significant.

Randomization

For the ViDAR study randomization will be supervised by the pharmacy at St Mary’s Hospital. The pharmacy will organise the packaging and have sole access to the randomization codes until the completion of all the clinical aspects of the study.

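### Appendix 4B curettes the left nostril 30 minutes before allergen challenge, so every later left-nostril mediator sample, and part of the symptom and mucosal readings, comes from freshly curetted mucosa

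*Combined protocol and SAP*

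**What the plan says.** Appendix 4B is the schedule for allergen Part B. Its curettage row begins "Nasal curettage X 4L", in the -30m column, and its only other entry is four right specimens at 6h. Nasosorption is taken from both nostrils at -30m, at -10m and at every time from 5m to 6h. The footnotes divide the analytes by side: "LEFT nostril: Nasosorption neat: to include from lipidomics, mass spectrometry, prostanoids, PGD2, tryptase" and "RIGHT nostril: Nasosorption in assay buffer: for chemokines and cytokines". The row "Total nasal symptom scores (TNSS) & PNIF" has a reading at -30m and none again until 5m. Mucosal examination is at -30m, at -10m and at every post-challenge time.

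Section 3.1 lists as an outcome "Inspection of nasal mucosa by a clinician: erythema, discharge, ulceration". Section 7 names cytokines and chemokines in the nasosorption eluates as its main data, and gives as one example of an area-under-the-curve analysis "e.g. PGD2 from 10min to 2h".

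Elsewhere the pre-challenge curettage is on an earlier day. Appendix 2b has "X Up to 4 samples" in its D -7 column, Appendix 2c has the same entry, and Appendices 3a and 3b also use D -7. Appendix 4A (ViDAR) has no pre-challenge curettage. For resiquimod, the Appendix 2c table places a left curettage at 6-8h, while the Appendix 2C diagram gives "Nasal curettage: d-7, 8h and 24h (up to 4/timepoint".

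**The concern.** Curettage removes tissue. Doing it four times in one nostril, half an hour before allergen is sprayed there, means that mediators later recovered from that nostril may reflect the curettage, the allergen, or a response to allergen that the curettage has altered. The analytes concerned include the early-phase mediators that the allergen model is meant to show. The clinician's inspection for redness, discharge and ulceration looks at the same mucosa. Because Appendix 4B gives everyone one schedule, no uncuretted comparison group exists from which to estimate and remove the effect at analysis.

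Symptoms and PNIF have a further problem. If the -30m reading precedes the curettage, change from baseline combines curettage and allergen. If it follows, the baseline is taken immediately after tissue removal. The table does not say which applies.

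**Working it through.** The plan states no figure on this point, so the check is a count of sampling times from the schedule tables. In the Appendix 4B and 2c rows used, the number of cells matches the header (16 of 16 and 12 of 12), so the entries have not shifted columns.

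**Appendix 4B, left curettage at -30m**

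- Nasosorption after challenge: 5m, 10m, 15m, 30m, 45m (5 times) and 1h to 6h (6 times), so 5 + 6 = 11. All follow the curettage.
- Nasosorption overall: 11 + 2 (at -30m and -10m) = 13 times. All but the -30m sample certainly follow, so 12 of 13. The -30m sample shares a slot with the curettage and its order is not given.
- Interval from curettage to sample: shortest 30 - 10 = 20 min (at -10m); longest 360 + 30 = 390 min = 6.5 h (at 6h).
- PGD2 window: starts 10 + 30 = 40 min and ends 120 + 30 = 150 min after curettage.
- Mucosal examination: all 11 post-challenge readings, and the one at -10m, follow.
- Symptoms and PNIF: 5m, 15m, 30m, 45m (4 times) and 1h to 6h (6 times), so 4 + 6 = 10, all following. These readings are not assigned to one nostril, so only part of the signal comes from the curetted side.
- Right-nostril cytokines and chemokines: no right curettage until the 6h slot, so nothing before 6h comes from a curetted nostril.
- Subjects (Section 3, Group 3 Part B): 12 + 12 + 6 + 16 = 46.

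**Comparison with the other schedules**

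| Schedule | Pre-challenge curettage |
|---|---|
| 2b, 2c, 3a, 3b | D -7 |
| 4A | none |
| 4B | -30m on the challenge day, left |

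**Appendix 2c, left curettage within 1-10h**

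- Curettage at 8h: left samples at 9h and 10h follow, so 2.
- Curettage at 6h: left samples at 7h, 8h, 9h and 10h follow, so 4.
- The 24h nasosorption cell has no side and is not counted as a left sample.

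**The case against.** The strongest reply is that the study's main data are spared: cytokines and chemokines come from the right nostril, and the PGD2 window is offered only as an example. That stands, and it limits the point to the neat-sample analytes, the mucosal inspection and part of the symptom and PNIF signal. A reader might infer that the whole allergen readout is compromised; the side assignments do not support that.

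Second, Appendix 4B has a bilateral washing lavage at -20m and a -10m sample after it, so mediators have a post-curettage baseline, and the challenge row covers saline as well as allergen. This stands for an additive effect. It does not deal with mucosa that responds differently to allergen because it was curetted, and symptoms and PNIF have no -10m reading. Section 1.2 intends a saline control, but Section 3 describes Part B as a single allergen dose and specifies no saline visit.

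Third, Section 1.1 describes a curettage specimen as pinhead-sized, and nothing in the documents measures its effect. That is correct, so no size of bias is claimed. The Appendix 4B diagram is also missing from the text available for this review, so the order within the -30m slot may be given there.

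Two other inferences should be resisted. The exclusions for nasal mucosal injury concern eligibility and say nothing about study sampling. Nor does Appendix 2c share the pre-challenge problem: its baseline curettage is at D -7 and its samples before 6h precede any same-day curettage. Its analyte legend is not printed, so which left analytes are affected there is an inference. Appendix 2b is not a fully clean comparator either, since it has an unsided 24h nasosorption after a 9h left curettage.

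**Conclusion.** The point holds for Appendix 4B. Followed as printed, the schedule puts the -10m left baseline and all 11 post-challenge left samples 20 minutes to 6.5 hours after four curettage specimens from the same nostril, in up to 46 subjects. It also puts every post-challenge mucosal inspection and, in part, every post-challenge symptom and PNIF reading after the curettage. Those results cannot be attributed to allergen alone.

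This rests on the curettage being done in its printed slot and on the footnoted side assignments. The direction and size of any distortion are unknown. The change is advisable and inexpensive, but the point does not undermine the right-nostril cytokine and chemokine results before 6h.

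The resiquimod point is secondary. Two curettage times need reconciling, and 2 to 4 late left samples need a stated handling.

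**What to change.** **Appendix 4B.** Move the -30m curettage to the screening visit, following Appendices 2b, 2c, 3a and 3b. Add a screening column to Appendix 4B and a curettage line to the Appendix 1 screening list. State that the 6h curettage follows the 6h nasosorption, mucosal examination and symptom/PNIF readings.

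The baseline specimen may stay on the left. Matching it to the right-sided 6h specimen would mean curetting the nostril that supplies the main cytokine and chemokine data, and the documents give no healing interval to show that this is harmless. The before/after curettage comparison therefore still changes nostril, and the report should say so.

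**Resiquimod.** Reconcile the Appendix 2c table with the 2C diagram to one fixed curettage time, used on both saline and resiquimod days. Either end the left-nostril time course at the curettage or analyse the later left samples separately. State the side of the 24h sample.

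**Cost.** Amendments to the two schedule tables, the Appendix 1 list and, where needed, the 2C diagram. No additional specimens are needed, and no additional visits because the screening visit already exists. The one scientific downside is that the allergen baseline specimen comes from a different day, so it should be taken at a similar clock time.
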